### 5.3.5.8 Deaths

All deaths that occur during the protocol-specified adverse event reporting period (see Section 5.3.1), regardless of relationship to study treatment, must be recorded on the Adverse Event eCRF and immediately reported to the Sponsor (see Section 5.4.2).

Death should be considered an outcome and not a distinct event. The event or condition that caused or contributed to the fatal outcome should be recorded as the single medical concept on the Adverse Event eCRF. Generally, only one such event should be reported. If the cause of death is unknown and cannot be ascertained at the time of reporting, **"unexplained death"** should be recorded on the Adverse Event eCRF. If the cause of death later becomes available (e.g., after autopsy), "unexplained death" should be replaced by the established cause of death. The term **"sudden death"** should not be used unless combined with the presumed cause of death (e.g., "sudden cardiac death").

Deaths that occur after the adverse event reporting period should be reported as described in Section 5.6.

### **5.3.5.9 Preexisting Medical Conditions**

A preexisting medical condition is one that is present at the screening visit for this study. Such conditions should be recorded on the General Medical History and Baseline Conditions eCRF.

A preexisting medical condition should be recorded as an adverse event only if the frequency, severity, or character of the condition worsens during the study. When recording such events on the Adverse Event eCRF, it is important to convey the concept that the preexisting condition has changed by including applicable descriptors (e.g., "more frequent headaches").

### **5.3.5.10 Lack of Efficacy or Worsening of Ulcerative Colitis**

Deterioration that is judged by the investigator to have unexpectedly worsened in severity or frequency or changed in nature (i.e., deterioration beyond the expected pattern of progression of the underlying disease) should be recorded as an adverse event. When recording an unanticipated worsening of ulcerative colitis on the Adverse Event eCRF, it is important to convey the concept that the condition has changed by including applicable descriptors (e.g., "accelerated worsening of ulcerative colitis"). Events that are clearly consistent with the expected pattern of progression of the underlying disease should not be recorded as adverse events. These data will be captured as efficacy assessment data only. In most cases, the expected pattern of progression will be based on the Mayo Score, which includes endoscopic disease evaluation. In rare cases, the determination of clinical progression will be based on symptomatic deterioration. However, every effort should be made to document progression through use of objective criteria. If there is any uncertainty as to whether an event is due to disease progression, it should be reported as an adverse event.

### **5.3.5.11 Hospitalization or Prolonged Hospitalization**

Any adverse event that results in hospitalization (i.e., inpatient admission to a hospital) or prolonged hospitalization should be documented and reported as a serious adverse event (per the definition of serious adverse event in Section 5.2.2), except as outlined below.

An event that leads to hospitalization under the following circumstances should not be reported as an adverse event or a serious adverse event:

- Hospitalization for respite care
- Hospitalization for a preexisting condition, provided that all of the following criteria are met:

The hospitalization was planned prior to the study or was scheduled during the study when elective surgery became necessary because of the expected normal progression of the disease

The patient has not experienced an adverse event

An event that leads to hospitalization under the following circumstances is not considered to be a serious adverse event, but should be reported as an adverse event instead:

- Hospitalization that was necessary because of patient requirement for outpatient care outside of normal outpatient clinic operating hours

#### **5.3.5.12 Patient-Reported Outcome Data**

Adverse event reports will not be derived from PRO data by the Sponsor. Sites are not expected to review the PRO data for adverse events.

#### **5.3.6 Special Situations (Accidental Overdose and/or Medication Error)**

Accidental overdose and medication error (**hereafter collectively referred to as "special situations"**), are defined as follows:

- Accidental overdose: accidental administration of a drug in a quantity that is higher than the assigned dose
- Medication error: accidental deviation in the administration of a drug (e.g., wrong drug, expired drug, accidental overdose, underdose, wrong dosing schedule, incorrect route of administration)

After initiation of study treatment, special situations associated with vixarelimab or matching placebo and any associated adverse events will be reported until [REDACTED] after the final dose of study treatment.

Special situations, regardless of whether they result in an adverse event, should be recorded on the Special Situations eCRF. If there are any associated adverse events, each event should be recorded separately on the Adverse Event eCRF.

Special situations and any associated adverse events should be reported within 30 days after the investigator becomes aware of the situation. However, if an associated adverse event fulfills seriousness criteria or qualifies as an adverse event of special interest, both the event and the special situation should be reported to the Sponsor immediately (i.e., no more than 24 hours after the investigator becomes aware of the event), as described in Section [5.4.2.2](#).

### **5.4 IMMEDIATE REPORTING REQUIREMENTS FROM INVESTIGATOR TO SPONSOR**

Certain events require immediate reporting to allow the Sponsor to take appropriate measures to address potential new risks in a clinical trial. The investigator must report such events to the Sponsor immediately; under no circumstances should reporting take place more than 24 hours after the investigator becomes aware of the event. The following is a list of events that the investigator must report to the Sponsor within

24 hours after the investigator becomes aware of the event, regardless of relationship to study treatment:

- Serious adverse events (defined in Section 5.2.2; see Section 5.4.2 for details on reporting requirements)
- Adverse events of special interest (defined in Section 5.2.3; see Section 5.4.2 for details on reporting requirements)
- Pregnancies (see Section 5.4.3 for details on reporting requirements)

For serious adverse events and adverse events of special interest, the investigator must report new significant follow-up information to the Sponsor immediately (i.e., no more than 24 hours after the investigator becomes aware of the information). New significant information includes the following:

- New signs or symptoms or a change in the diagnosis
- Significant new diagnostic test results
- Change in causality based on new information
- Change in the event's outcome, including recovery
- Additional narrative information on the clinical course of the event

Investigators must also comply with local requirements for reporting serious adverse events to the local health authority and IRB/EC.

#### **5.4.1            Emergency Medical Contacts**

To ensure the safety of study participants, access to the Medical Monitors is available 24 hours per day, 7 days per week. Details will be provided separately.

#### **5.4.2            Reporting Requirements for Serious Adverse Events and Adverse Events of Special Interest**

##### **5.4.2.1        Events That Occur prior to Study Treatment Initiation**

After informed consent has been obtained but prior to initiation of study treatment, only serious adverse events caused by a protocol-mandated intervention should be reported. The paper Clinical Trial Adverse Event/Special Situations Form provided to investigators should be completed and submitted to the Sponsor or its designee immediately (i.e., no more than 24 hours after the investigator becomes aware of the event), either by faxing or by scanning and emailing the form using the fax number or email address provided to investigators.

##### **5.4.2.2        Events That Occur after Study Treatment Initiation**

After initiation of study treatment, serious adverse events and adverse events of special interest will be reported until [REDACTED] after the final dose of study treatment. Investigators should record all case details that can be gathered immediately (i.e., within 24 hours after the investigator becomes aware of the event) on the Adverse Event eCRF

and submit the report via the electronic data capture (EDC) system. A report will be generated and sent to Safety Risk Management by the EDC system.

In the event that the EDC system is unavailable, the paper Clinical Trial Adverse Event/Special Situations Form provided to investigators should be completed and submitted to the Sponsor or its designee immediately (i.e., no more than 24 hours after the investigator becomes aware of the event), either by faxing or by scanning and emailing the form using the fax number or email address provided to investigators. Once the EDC system is available, all information will need to be entered and submitted via the EDC system.

Instructions for reporting serious adverse events that occur [REDACTED] after the final dose of study treatment are provided in Section 5.6.

### **5.4.3      Reporting Requirements for Pregnancies**

#### **5.4.3.1      Pregnancies in Female Patients**

Female patients will be instructed through the Informed Consent Form to immediately inform the investigator if they become pregnant during the study or within [REDACTED] after the final dose of study treatment. A paper Clinical Trial Pregnancy Reporting Form should be completed and submitted to the Sponsor or its designee immediately (i.e., no more than 24 hours after learning of the pregnancy), either by faxing or by scanning and emailing the form using the fax number or email address provided to investigators. Pregnancy should not be recorded on the Adverse Event eCRF. The investigator should discontinue study treatment and counsel the patient, discussing the risks of the pregnancy and the possible effects on the fetus. Monitoring of the patient should continue until conclusion of the pregnancy. Any serious adverse events associated with the pregnancy (e.g., an event in the fetus, an event in the mother during or after the pregnancy, or a congenital anomaly/birth defect in the child) should be reported on the Adverse Event eCRF. In addition, the investigator will submit a Clinical Trial Pregnancy Reporting Form when updated information on the course and outcome of the pregnancy becomes available.

Attempts should be made to collect and report infant health information. When permitted by the site, an Authorization for the Use and Disclosure of Infant Health Information would need to be signed by one or both parents (as per local regulations) to allow for follow-up on the infant. If the authorization has been signed, the infant's health status at birth should be recorded on the Clinical Trial Pregnancy Reporting Form. In addition, the Sponsor may collect follow-up information on the infant's health status at 6 and 12 months after birth.

#### **5.4.3.2      Pregnancies in Female Partners of Male Patients**

Male patients will be instructed through the Informed Consent Form to immediately inform the investigator if their partner becomes pregnant during the study or within [REDACTED] after the final dose of study treatment. The investigator should report the

pregnancy on the paper Clinical Trial Pregnancy Reporting Form and submit the form to the Sponsor or its designee immediately (i.e., no more than 24 hours after learning of the pregnancy), either by faxing or by scanning and emailing the form using the fax number or email address provided to investigators. Attempts should be made to collect and report details of the course and outcome of any pregnancy in the partner of a male patient exposed to study treatment. When permitted by the site, the pregnant partner would need to sign an Authorization for the Use and Disclosure of Pregnancy Health Information to allow for follow-up on her pregnancy. If the authorization has been signed, the investigator should submit a Clinical Trial Pregnancy Reporting Form with additional information on the pregnant partner and the course and outcome of the pregnancy as it becomes available.

Attempts should be made to collect and report infant health information. When permitted by the site, an Authorization for the Use and Disclosure of Infant Health Information would need to be signed by one or both parents (as per local regulations) to allow for follow-up on the infant. If the authorization has been signed, the infant's health status at birth should be recorded on the Clinical Trial Pregnancy Reporting Form. In addition, the Sponsor may collect follow-up information on the infant's health status at 6 and 12 months after birth.

An investigator who is contacted by the male patient or his pregnant partner may provide information on the risks of the pregnancy and the possible effects on the fetus, to support an informed decision in cooperation with the treating physician and/or obstetrician.

#### **5.4.3.3 Abortions**

A spontaneous abortion in a female patient exposed to study treatment or the female partner of a male patient exposed to study treatment should be classified as a serious adverse event (as the Sponsor considers abortions to be medically significant), recorded on the Adverse Event eCRF, and reported to the Sponsor immediately (i.e., no more than 24 hours after the investigator becomes aware of the event; see Section 5.4.2).

If a therapeutic or elective abortion was performed because of an underlying maternal or embryofetal toxicity, the toxicity should be classified as a serious adverse event, recorded on the Adverse Event eCRF, and reported to the Sponsor immediately (i.e., no more than 24 hours after the investigator becomes aware of the event; see Section 5.4.2). A therapeutic or elective abortion performed for reasons other than an underlying maternal or embryofetal toxicity is not considered an adverse event.

All abortions should be reported as pregnancy outcomes on the paper Clinical Trial Pregnancy Reporting Form.

#### **5.4.3.4 Congenital Anomalies/Birth Defects**

Any congenital anomaly/birth defect in a child born to a female patient exposed to study treatment or the female partner of a male patient exposed to study treatment should be classified as a serious adverse event, recorded on the Adverse Event eCRF, and reported to the Sponsor immediately (i.e., no more than 24 hours after the investigator becomes aware of the event; see Section 5.4.2).

### **5.5 FOLLOW-UP OF PATIENTS AFTER ADVERSE EVENTS**

#### **5.5.1 Investigator Follow-Up**

The investigator should follow each adverse event until the event has resolved to baseline grade or better, the event is assessed as stable by the investigator, the patient is lost to follow-up, or the patient withdraws consent. Every effort should be made to follow all serious adverse events considered to be related to study treatment or trial-related procedures until a final outcome can be reported.

During the adverse event reporting period (defined in Section 5.3.1), resolution of adverse events (with dates) should be documented on the Adverse Event eCRF and in the patient's medical record to facilitate source data verification.

All pregnancies reported during the study should be followed until pregnancy outcome, with follow-up information on the infant collected according to procedures outlined in Section 5.4.3.

#### **5.5.2 Sponsor Follow-Up**

For serious adverse events, adverse events of special interest, and pregnancies, the Sponsor or a designee may follow up by telephone, fax, email, and/or a monitoring visit to obtain additional case details and outcome information (e.g., from hospital discharge summaries, consultant reports, autopsy reports) in order to perform an independent medical assessment of the reported case.

### **5.6 ADVERSE EVENTS THAT OCCUR AFTER THE ADVERSE EVENT REPORTING PERIOD**

The Sponsor should be notified if the investigator becomes aware of any serious adverse event that occurs after the end of the adverse event reporting period (defined as [REDACTED] after the final dose of study treatment), if the event is believed to be related to prior exposure to study treatment. These events should be reported through use of the Adverse Event eCRF. However, if the EDC system is not available, the investigator should report these events directly to the Sponsor or its designee, either by faxing or by scanning and emailing the paper Clinical Trial Adverse Event/Special Situations Form using the fax number or email address provided to investigators.

## **5.7 EXPEDITED REPORTING TO HEALTH AUTHORITIES, INVESTIGATORS, INSTITUTIONAL REVIEW BOARDS, AND ETHICS COMMITTEES**

The Sponsor will promptly evaluate all serious adverse events and adverse events of special interest against cumulative product experience to identify and expeditiously communicate possible new safety findings to investigators, IRBs, ECs, and applicable health authorities based on applicable legislation.

To determine reporting requirements for single adverse event cases, the Sponsor will assess the expectedness of these events through use of the reference safety information in the document listed below:

Drug	Document
Vixarelimab	Vixarelimab Investigator's Brochure

The Sponsor will compare the severity of each event and the cumulative event frequency reported for the study with the severity and frequency reported in the applicable reference document.

Reporting requirements will also be based on the investigator's assessment of causality and seriousness, with allowance for upgrading by the Sponsor as needed.

An Internal Monitoring Committee (IMC) will monitor the incidence of the above-listed anticipated events during the study. An aggregate report of any clinically relevant imbalances that do not favor the test product will be submitted to health authorities.

## **6. STATISTICAL CONSIDERATIONS AND ANALYSIS PLAN**

The primary analyses of efficacy and safety data will be performed after all enrolled patients have either completed the [REDACTED] visit or have discontinued from the study prior to [REDACTED], and all data from this period are in the database and have been cleaned and verified. The final analyses of complete data for the study will be performed when all enrolled patients have either completed the safety follow-up period or discontinued early from the study, all data from the study are in the database, and the database is locked. Detailed specifications of the statistical methods will be described in the Data Analysis Plan (DAP).

### **6.1 DETERMINATION OF SAMPLE SIZE**

Approximately 210 patients will be enrolled in this study. [REDACTED]

[REDACTED] Eligible patients will be randomized in a [REDACTED] to vixarelimab [REDACTED] arm, vixarelimab [REDACTED] arm, or placebo [REDACTED] arm during the induction period [REDACTED]

## **6.2 SUMMARIES OF CONDUCT OF STUDY**

The number of patients who enroll, discontinue (early discontinuation of treatment or early termination from the study), or complete the study will be summarized. Reasons for premature treatment discontinuation or early termination from the study will be listed and summarized. Enrollment and major protocol deviations will be listed and evaluated for their potential effects on the interpretation of study results.

## **6.3 SUMMARIES OF DEMOGRAPHIC AND BASELINE CHARACTERISTICS**

Demographic and baseline characteristics (including, but not limited to, age, sex, race/ethnicity) will be summarized using means, standard deviations, medians, and ranges for continuous variables and proportions for categorical variables, as appropriate. Summaries will be presented overall and by treatment group.

## **6.4 EFFICACY ANALYSES**

The analysis population for the efficacy analyses will be the modified intent-to-treat population defined as all patients who received at least one dose of study treatment and have at least one postbaseline efficacy measurement, with patients grouped according to their assigned treatment.

Because the study is hypothesis-generating in nature, hypothesis testing will be carried out in an exploratory fashion, at a two-sided 0.20 significance level. [REDACTED]

[REDACTED]. A separate DAP will contain more details on the statistical analyses.

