## 4.2 METHOD OF TREATMENT ASSIGNMENT AND BLINDING

### 4.2.1 Treatment Assignment

This is a three-arm randomized study. After initial written informed consent has been obtained, all screening procedures and assessments have been completed, and eligibility has been established for a patient, the study site will obtain the patient's treatment assignment from an interactive voice or web-based response system (IxRS).

Patients will be randomly assigned to one of three treatment arms: the vixarelimab [REDACTED] arm, vixarelimab [REDACTED] arm, or placebo arm in a [REDACTED] ratio. Randomization will occur through use of a permuted-block randomization method to ensure a [REDACTED]. Randomization will be stratified by advanced or conventional failure and baseline mMS [REDACTED]. During the optional ATE period, patients assigned to the vixarelimab [REDACTED] arm or the vixarelimab [REDACTED] arm during the induction period will continue on the randomized treatment assignment; patients treated with placebo during the induction period will receive vixarelimab [REDACTED] (see Section 3.1.1 for further details).

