#### **Stool Frequency and Rectal Bleeding**

Stool frequency and rectal bleeding are components of the Mayo Score and mMS.

At screening, the patient's normal number of stools, defined as the number of stools passed when a patient is in remission (i.e., not in flare), or prior to the onset of UC if a patient has never been in remission, will be documented.

Patients are to record stool frequency and rectal bleeding daily in their electronic diary (e-diary) during screening and induction, beginning with the first screening visit, and at specified timepoints throughout the study (see [Appendix 1](#) and [Appendix 2](#)). The average stool frequency and rectal bleeding scores from the daily e-diary entries within the [REDACTED] will be used as efficacy baseline and for inclusion. [REDACTED]

[REDACTED]

[REDACTED] If the average stool frequency and rectal bleeding scores are not available from the [REDACTED] the average stool frequency and rectal bleeding scores from the [REDACTED] will be used as the baseline for efficacy assessment and for inclusion.

Because the endoscopy and associated bowel preparation can interfere with the assessment of PROs, e-diary entries on days of bowel preparation, endoscopy, and the day after endoscopy will not be used to calculate any stool frequency or rectal bleeding scores.

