### **6.4.1 Primary Efficacy Endpoint**

The primary efficacy endpoint is clinical remission at Week 12 (see definition of clinical remission in Section 2). A comparison between the vixarelimab arms and the placebo arm will be carried out. The difference between vixarelimab arms versus placebo arm in the proportion of patients with clinical remission at Week 12 will be evaluated by the Cochran-Mantel-Haenszel test, stratified by advanced or conventional failure and baseline mMS [REDACTED]. The non-responder imputation method, where subjects with missing data at scheduled assessment visits will be considered as “not achieved” for the clinical remission, will be used for primary analysis. A subgroup (advanced failure) analysis for the primary efficacy endpoint will be conducted *using the same methods outlined above, except that the Cochran-Mantel-Haenszel test will be stratified by baseline mMS [REDACTED]*.

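### The efficacy population removes dosed patients with no postbaseline efficacy measurement before non-responder imputation can count them as failures, so the remission difference can be biased in either direction

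*Combined protocol and SAP*

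**What the plan says.** Section 6.4 defines one modified intent-to-treat population for all efficacy analyses: "all patients who received at least one dose of study treatment and have at least one postbaseline efficacy measurement", grouped by assigned treatment. The sentence is complete and unredacted.

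Section 6.4.1 states: "The primary efficacy endpoint is clinical remission at Week 12". The comparison of the vixarelimab arms with placebo "will be evaluated by the Cochran-Mantel-Haenszel test, stratified by advanced or conventional failure and baseline mMS" (the cut-point is redacted). For the primary analysis, "subjects with missing data at scheduled assessment visits will be considered as" not having achieved remission, which is non-responder imputation. The advanced failure analysis uses the same methods, stratified by baseline modified Mayo Score (mMS) only. Table 1 lists advanced failures under the primary objective.

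Testing is exploratory, "at a two-sided 0.20 significance level". Further detail is left to a separate Data Analysis Plan (DAP), which is not among the documents. The safety population in Section 6.5 is all randomized patients who received a dose, with no measurement condition.

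**The concern.** The two rules conflict for one group: patients who were dosed and then left before giving any postbaseline efficacy measurement. Section 6.4.1 has an answer for them (non-remission), but Section 6.4 removes them before it can be used. No visible passage brings them back or plans a sensitivity analysis in all dosed or all randomized patients.

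The measurement condition does no useful work here. The endpoint is binary and every missing value has an assigned outcome, so each dosed patient can be classified without postbaseline data. The condition does, however, depend on events after randomization, such as early exit for an adverse event, worsening or refusal. These can occur at different rates by arm, and patients who stop or withdraw are not replaced (Sections 4.6.1 and 4.6.2). At stake are the remission rates and their difference, overall and in advanced failures. The secondary proportions in Section 6.4.2 use the same population.

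**Working it through.** **Inputs from the protocol.** "Approximately 210 patients will be enrolled in this study" (Section 6.1). "This is a three-arm randomized study" (Section 4.2.1). Two-sided level 0.20 (Section 6.4).

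**Assumptions, not from the protocol.** The allocation ratio is redacted, and no remission or dropout rates are visible. I take 70 per arm (210/3), with 84 versus 42 as a check, and ignore stratification. The plan states no figure on this point to reproduce.

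**Step 1: effect on one arm.** With x remitters among n dosed patients, non-responder imputation gives x/n. Removing k non-remitters gives x/(n - k), so the rate is multiplied by n/(n - k).

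- n = 70: k = 1 gives 70/69 = 1.014, so 14/70 = 20.0% becomes 14/69 = 20.3%. k = 4 gives 1.061; k = 7 gives 1.111.
- Smaller denominators are more sensitive: k = 3 gives 70/67 = 1.045 in an arm of 70, but 35/32 = 1.094 in an assumed advanced failure arm of 35.

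**Step 2: effect on the difference.** Let pA and pP be remission in all dosed patients, and eA and eP the shares excluded. The written population estimates D = pA/(1 - eA) - pP/(1 - eP). With pA = 20% and pP = 7%, the all-dosed difference is 13.0 points.

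| Excluded, active / placebo | Active | Placebo | Difference | Change |
|---|---|---|---|---|
| 0% / 10% | 20.0% | 7.8% | 12.2 | -0.8 |
| 4% / 10% | 20.8% | 7.8% | 13.1 | +0.1 |
| 10% / 10% | 22.2% | 7.8% | 14.4 | +1.4 |
| 10% / 4% | 22.2% | 7.3% | 14.9 | +1.9 |
| 15% / 5% | 23.5% | 7.4% | 16.2 | +3.2 |

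**Step 3: effect on the test.** Pooled two-proportion z-test, 70 per arm, 14 versus 7 remitters:

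- None excluded: 20.0% vs 10.0%, difference 10.0 points, z = 1.657, p = 0.098.
- 7 excluded in each arm: 22.2% vs 11.1%, difference 11.1, z = 1.673, p = 0.094.
- 7 excluded from active only: 22.2% vs 10.0%, difference 12.2, z = 1.930, p = 0.054.
- 7 excluded from placebo only: 20.0% vs 11.1%, difference 8.9, z = 1.404, p = 0.160.

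Excluding an equal share e from both arms scales the difference by 1/(1 - e), but it multiplies z only by the square root of (1 - p)/(1 - p/(1 - e)), where p is the pooled rate. With p = 0.15 and e = 0.10 this is sqrt(0.85/0.8333) = 1.010.

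Check at 84 versus 42 with 17 vs 4 remitters: excluding 7 from active only moves p from 0.128 to 0.086.

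**Step 4: no true difference.** With 10% remission in both arms of 70 and 400,000 simulated trials, the chance of a significant result favoring active (nominal 10% per side) is 10.6% with all dosed patients counted. It becomes 12.4% with 4 vs 0 excluded (active vs placebo), 14.0% with 7 vs 1, and 15.1% with 7 vs 0. With 7 vs 0 the total two-sided rate moves only from 21.1% to 22.0%, so the error mainly shifts toward one side.

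**The case against.** The strongest case for leaving the text alone has four parts.

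*Few patients may be affected.* The condition asks for one measurement of any kind. Section 4.5.7.2 says "Patients are to record stool frequency and rectal bleeding daily in their electronic diary (e-diary) during screening and induction", and diary averages also serve as the efficacy baseline. On that reading, only patients with no diary entry or other efficacy assessment after dosing are lost. This is a fair reading, perhaps the more natural one, and the effect would then be small. It is not written down, however, and the choice should not be made once data are visible.

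*The bias need not favor the drug.* A reader might infer that the difference is usually inflated. The documents do not support this, because they give no dropout figures by arm. If worsening removes more placebo patients, the difference can shrink, as the first row of the Step 2 table shows. At 20% versus 7% a fall needs eP/(1 - eP) to exceed eA/(1 - eA) by more than 20/7 = 2.9 times. When true rates are equal, the direction depends only on which arm loses the larger share.

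*The primary analysis does not become close to complete-case.* A reader might infer that it does if an mMS or endoscopy is required. But patients who stop treatment are to attend a discontinuation visit (Section 4.6.1), and endoscopy is scheduled there (Section 4.5.6). Those who have it stay in the population and count as failures if Week 12 is missing. Only patients with no qualifying postbaseline measurement at all leave.

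*The stakes are limited.* The study is described as hypothesis-generating. At 20% versus 7% with 70 per arm, the standard error of the difference is sqrt(0.20 x 0.80/70 + 0.07 x 0.93/70) = 5.7 points, so the largest shift shown (3.2) is a little over half of it. The DAP or redacted text might define the term or add an all-dosed analysis. This lowers the severity. It does not remove the conflict, and a DAP should not have to override the protocol's population.

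**Conclusion.** Wrong as written, and it should be fixed. The population rule in Section 6.4 overrides the imputation rule in Section 6.4.1 for dosed patients with no postbaseline efficacy measurement. It does so through a post-randomization condition that can differ by arm.

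The direction is not determined by the documents. Across the illustrative scenarios (70 per arm, 20% vs 7%, 0% to 15% excluded) the change runs from about -0.8 to +3.2 points. It is far smaller if a single diary entry counts. Equal exclusion inflates the estimate but barely affects the p-value; a material effect on the test needs clearly unequal exclusion. All rates and exclusion shares are assumptions, so these figures show sensitivity and are not forecasts. With exploratory testing at two-sided 0.20, this is a should-fix point and does not invalidate the study.

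**What to change.** In Section 6.4, delete the second condition (the postbaseline efficacy measurement) from the population definition. Define the efficacy population as all randomized patients who received at least one dose, grouped as assigned. State that non-responder imputation applies to all of them, overall and in the advanced failure analysis, and carry the same definition into the DAP. If the term efficacy measurement is kept anywhere, define it before unblinding.

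The cost is one sentence in the protocol and its counterpart in the DAP. No new data or visits are needed, and the population then matches the safety population in Section 6.5 except that patients are grouped as assigned. Stated remission rates will be slightly lower in any arm with patients who would otherwise have been excluded.
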